## **Enrollment/Randomization**

Sample sizes of 22, 22, and 22 will be allocated to 3 groups (control, aspiration, and aspiration plus injection) using an equal 1:1:1 block randomized allocation.

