## **Study Procedures**

We propose to study all tibial plateau fractures treated at LUHS for which we have fracture data, treated with ORIF or treated non-operatively. Patients will be identified based on the classification of their injury, that being tibial plateau fracture; we will seek to sub-classify each patient based on the Shatzker classification of tibial plateau fractures and using OA classification as our prospective study will be based on both tibial plateau fractures as a whole and their sub-classification: lateral tibial plateau fracture without depression (I), lateral tibial plateau fracture with depression (II), compression fracture of the lateral (IIIA) or central (IIIB) tibial plateau, medial tibial plateau fracture (IV), bicondylar tibial plateau fracture (V), and tibial plateau fracture with diaphyseal discontinuity (VI). It is important for our prospective study to classify each fracture pattern as they generally differ in energy of injury and thus may affect pain management or need for narcotic pain medications and also potentially affect functional outcomes. Patient inclusion will be based on agreement to participate using informed consent. Additionally, patients may be excluded from the study if they choose not to consent, are incapacitated on initial presentation, have an emergent condition necessitating either operative management or airway protection or have a history of allergic reaction to local anesthetic injection.

Following consent for participation in the study, patients will be blinded to initial management of the tibial plateau fracture with either: Aspiration of the joint alone, aspiration of the knee joint and injection of 20cc bupivacaine 0.5% with 1:200,000 epinephrine or no injection or aspiration therapy for a control arm. Using the block randomization list, the patient will be randomized at the time of consent for participation. For the sake of consistency, all participating treating physicians (orthopaedic on-call residents) will be trained on Sawbones™ Fully Encased Knee Joint with Patella and Ligaments for a standardized aspiration and injection technique.

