For the patients randomized into the treatment arms, the knee will be held in 15-30\* short of full extension and fully prepped using chlorhexidine wipes in a centrifugal manner. An 18 gauge spinal needle will be introduced into the superolateral aspect of the knee (if the knee is too edematous, an inferolateral or inferomedial approach is appropriate, but requires documentation). Aspirate the knee with 60cc syringe until unable to draw out more fluid and record volume on

given study form. Remove the syringe from the needle connection, leaving the 18 gauge needle in place. Draw up 30cc of 0.5% bupivacaine with 1:200,000 epinephrine (Marcaine) with .18-gauge needle into 2nd 60cc syringe. Place the filled syringe on the 18 gauge needle already in the knee and INJECT. Remove needle-syringe construct and place bandage over injection site.

The patient's initial NRS score will be recorded immediately. Subsequent VAS scores will be recorded at time points 0 (5 minutes after intervention), 2, 4, 6, 8, 12, 24 hours after initial work-up of the patient. Patients treated as an outpatient will record these values themselves (copy of recording form submitted with this application). Patients will be directed to bring the completed form with them to their regular clinic follow-up visit. Additionally, supplemental analgesia requirements will be recorded upon administration and will be converted to morphine equivalent units for analysis (copy of recording form submitted with this application). All patients admitted to the orthopedic service will be placed on morphine PCA (determined dosing by weight of patient). All other patients (those admitted to other services) will have analgesia converted to Opioid Morphine Equivalents (OMEs).

Prospectively: Patients will be blinded to initial management of the tibial plateau fracture with either: Aspiration of the knee joint alone, aspiration of the joint and injection of bupivacaine 0.5% with epinephrine or no injection or aspiration therapy for a control arm. Using the block randomization list, the patient will be randomization at the time of consent for participation. The patient's initial VAS score will be recorded at the time of initial work-up. Subsequent VAS scores will be recorded at time points 2, 4, 6, 8, 12, 24 hours after initial work-up of the patient. Additionally, supplemental analgesia requirements will be recorded upon administration and will be converted to morphine equivalent units for analysis.

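### The experimental injection is given as 20cc in one place and 30cc in another, and the procedure steps have no stopping point for the aspiration-only arm

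*Combined protocol and SAP*

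**What the plan says.** The design has "3 groups (control, aspiration, and aspiration plus injection) using an equal 1:1:1 block randomized allocation", with 22 patients per group (Enrollment/Randomization, repeated in Statistical Considerations).

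Study Procedures then describes the third arm three times:

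- The arm description gives "aspiration of the knee joint and injection of 20cc bupivacaine 0.5% with 1:200,000 epinephrine". The same paragraph says that all treating on-call residents will be trained on a knee model "for a standardized aspiration and injection technique".
- The technique steps open with "For the patients randomized into the treatment arms, the knee will be held in" slight flexion. After the aspiration they continue "Draw up 30cc of 0.5% bupivacaine with 1:200,000 epinephrine (Marcaine" and then "Place the filled syringe on the 18 gauge needle already in the knee and INJECT".
- The closing paragraph, which begins with the word Prospectively, restates the procedural arms as "Aspiration of the knee joint alone, aspiration of the joint and injection of bupivacaine 0.5% with epinephrine" and gives no volume.

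**The concern.** The injected solution is the experimental treatment, and the protocol defines it in two ways that cannot both be followed. Several on-call residents will deliver it. Unless something outside the document settles the volume, different operators could give different doses under the same protocol. The trial would then estimate an average effect over an unknown mix of doses. Even if everyone gives the same volume, a reader of the protocol could not say what was tested.

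The second part concerns the aspiration-only arm. Aspiration alone against aspiration plus injection is the only comparison that separates the effect of bupivacaine from the effect of draining the joint. The Background shows why that separation matters. One cited elbow-fracture study found no added benefit of bupivacaine over aspiration, and another found that aspiration itself relieved pain. An operator who followed the steps literally would inject the aspiration-only patients too, and the comparison would be lost.

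**Working it through.** The plan states no total dose in milligrams, so there is no figure to reproduce. The check compares the texts and converts volume to dose.

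**1. Is it the same solution?** Yes. Both places in Study Procedures specify 0.5% bupivacaine with 1:200,000 epinephrine, so only the volume differs.

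**2. What does each volume deliver?** A 0.5% solution is 0.5 g per 100 mL, or 5 mg/mL. A 1:200,000 solution is 1 g per 200,000 mL, or 5 micrograms/mL. Dose = volume × concentration.

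| | Arm description (20cc) | Technique steps (30cc) | Difference | Ratio |
|---|---|---|---|---|
| Bupivacaine | 20 × 5 = 100 mg | 30 × 5 = 150 mg | 50 mg | 1.5 |
| Epinephrine | 20 × 5 = 100 micrograms | 30 × 5 = 150 micrograms | 50 micrograms | 1.5 |

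**3. Could the operator be meant to draw up 30cc and give 20cc?** The text does not support this. The next instruction attaches the filled syringe to the needle and injects, and no partial volume is stated.

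**4. Does other text settle the volume?** No.

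- The closing paragraph of Study Procedures gives no volume.
- Preliminary Studies 2.1 mentions 30 ml, but that is the regimen of a cited knee-replacement study.
- Both conflicting figures stand in current text; neither comes from an amendment log.

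**5. What if both knees are treated?** The Inclusion Criteria admit bilateral tibial plateau fractures, and the protocol does not say whether one or both knees would be injected. If both were, the totals would be 2 × 100 = 200 mg against 2 × 150 = 300 mg. The gap doubles from 50 to 100 mg, and the ratio stays at 1.5.

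**6. Do the steps branch by arm?** Two of the three arms involve a needle: aspiration, and aspiration plus injection. The steps address the treatment arms in the plural and go from aspiration, to removing the syringe with the needle left in place, to drawing up bupivacaine, to injecting. Needle removal and bandaging come only after the injection, so the aspiration-only arm has no end point. Read literally, 22 + 22 = 44 of 66 patients would be injected instead of 22. Every definition of the arms contradicts that reading (Enrollment/Randomization, both descriptions in Study Procedures, and Statistical Considerations).

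**The case against.** The strongest reply accepts the conflict in volume and disputes its consequences.

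- *Training may already impose one volume.* All operators are to be trained in a standard technique, and the training material is not in the documents. Uniform practice, with one of the two texts simply wrong, is quite plausible. This stands as a limit on the mixed-dose argument, which is a possibility and not a demonstrated fact. It does not remove the problem, because training has to follow one of two conflicting texts.
- *Mixed volumes would not bias the randomised comparison.* This is correct. The comparison would estimate an average over the volumes given. The harm is to the definition and reproducibility of the treatment. With 22 patients in the arm, a mix could not be untangled reliably afterwards.
- *The aspiration-only arm is clearly defined elsewhere.* This also stands. The opening phrase can be read as introducing only the preparation and aspiration that both arms share. The missing branch is therefore an omission in the steps, not a dispute about which arms exist.
- *No hazard is shown.* The Risks section states that no systemic problems have been reported after a single intra-articular knee injection of local anesthetic, and the documents give no maximum dose. Nothing here shows either volume to be unsafe. The safety point is only that a dose should not be ambiguous, and the Risks statement does not address injection of both knees.
- *The form may already record the injected volume.* The form is not in the documents, so this cannot be excluded. The procedure text asks for a volume to be recorded only at the aspiration step.

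**Conclusion.** The concern holds and must be fixed. The protocol gives two irreconcilable volumes of the same solution for its experimental arm, differing by 10cc, 50 mg of bupivacaine and 50 micrograms of epinephrine, a ratio of 1.5. This rests only on the wording of Study Procedures and on the standard meaning of the stated concentrations. It is an internal inconsistency in the definition of the treatment.

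The missing aspiration-only branch is a real but secondary gap, since the intended allocation is clear from the rest of the document. Two consequences remain conditional: mixed dosing depends on what operators are actually taught, and the doubled gap depends on both knees being injected.

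**What to change.** 1. The investigators decide on one volume and reconcile the two passages of Study Procedures. The same volume then goes into every description of the arm, including the closing paragraph that now gives none, and into the training material. Which volume is right is for the investigators to determine.
2. Write the technique steps by arm: shared preparation and aspiration, then an explicit end point for aspiration alone, then the injection steps for aspiration plus injection only.
3. State how patients with bilateral fractures are handled, so that the total dose is defined for them too.
4. Record on the study form the volume actually injected, if it is not already captured.

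The cost is protocol wording, a corrected training sheet and at most one form field. Sample size, randomisation and assessment schedule do not change. If patients have already been treated, the volume each received should be retrieved where records allow and reported.

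### Opioid orders outside the orthopaedic PCA rule can be written with the arm known, so the Aim 2 opioid total may partly reflect staff expectation; entering initial orders before allocation is a cheap improvement

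*Combined protocol and SAP*

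**What the plan says.** All the relevant text is in the Study Procedures section of the combined protocol and SAP.

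- **Blinding.** After consent, "patients will be blinded to initial management of the tibial plateau fracture". No other role is described as blinded.
- **Timing of allocation.** "Using the block randomization list, the patient will be randomized at the time of consent for participation". No step places analgesic orders before the allocation is known.
- **Operators.** For a standardized technique, "all participating treating physicians (orthopaedic on-call residents) will be trained on" a knee model. Whoever aspirates or injects knows the arm, and the plan calls these residents treating physicians.
- **Opioid ordering.** The only rule is "All patients admitted to the orthopedic service will be placed on morphine PCA (determined dosing by weight of patient".
- **Other services.** "All other patients (those admitted to other services) will have analgesia converted to Opioid Morphine Equivalents (OMEs". This makes the units comparable but does not govern what is ordered.
- **Patients sent home.** They fill in their own record of the study values. The text gives no rule for their opioid prescription.

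Specific Aim 2 (Rationale and Specific Aims) asks whether patients who have aspiration plus bupivacaine use less supplemental opioid, and its working hypothesis is a reduction.

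**The concern.** Opioid consumption depends on pain, but also on what has been ordered. Where the prescriber knows the arm and expects the needle to help, a smaller order or prescription is a natural response. That lowers the recorded total in the direction of the Aim 2 hypothesis even if pain is unchanged. Complete dose recording does not protect against this: it captures the lower total but not the reason for it, and no later analysis could separate the two.

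Three parts of the Aim 2 total lie outside the PCA rule:

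1. opioid given to orthopaedic admissions between allocation and the start of PCA;
2. intake at home, which is limited by the discharge prescription but also chosen by the patient;
3. opioid ordered by other admitting services.

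**Working it through.** **The plan's own figure.** There is none for Aim 2: no test, SD or power is given. The one power figure, 84% in Statistical Considerations, concerns the 24-hour pain score and is not used here. The only input below taken from the plan is 22 patients per arm. Everything else is assumed, so this is a sensitivity calculation and not an estimate.

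**Assumed inputs (range; midpoint)**

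| Symbol | Meaning | Range | Midpoint |
|---|---|---|---|
| po | share admitted to other services | 0 to 20% | 0.10 |
| ph | share sent home | 10 to 30% | 0.20 |
| e | share of orthopaedic patients' opioid given between allocation and PCA start | 0 to 20% | 0.10 |
| k | mean opioid off PCA relative to on PCA | 0.5 to 1.5 | 1 |
| r | staff-driven reduction in a needle arm, none in control | 10 to 30% | 0.20 |
| h | fraction of r that applies to patients sent home | 25 to 75% | 0.5 |

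**Step 1: spurious fall in an arm mean.**

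fall = [(1 − po − ph)·e·r + k·po·r + k·ph·r·h] / [(1 − po − ph) + k·(po + ph)]

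At the midpoints:

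- before PCA: 0.70 × 0.10 × 0.20 = 0.014
- other services: 1 × 0.10 × 0.20 = 0.020
- sent home: 1 × 0.20 × 0.20 × 0.5 = 0.020
- denominator: 0.70 + 1 × 0.30 = 1.00

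fall = 0.054, or 5.4%.

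**Step 2: plausible spread.** Drawing the six inputs independently and uniformly over their ranges, the central 95% of the fall runs from about 1.8% to 10.5%. Results with every input at one extreme together lie outside this interval and are not used.

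**Step 3: effect on the error rate.** Assume a two-sided two-sample t-test at 5% (df = 42, critical value 2.018) and an opioid coefficient of variation (CV) of 0.5 or 1.0.

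- SE of the relative difference = CV × √(2/22) = 0.151 (CV 0.5) or 0.302 (CV 1.0).
- Noncentrality at the midpoint = 0.054/0.151 = 0.36, or 0.054/0.302 = 0.18.
- Rejection probability with no true effect, from the noncentral t: 6.4% (CV 0.5) or 5.4% (CV 1.0).
- At the upper end of the Step 2 interval, noncentrality is 0.105/0.151 = 0.70 or 0.105/0.302 = 0.35, giving 10.5% or 6.3%.

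**Step 4: how much the fix can reach.** If the orders before PCA and at discharge can be entered in advance, the reachable part is 0.014 + 0.020 = 0.034, and 3.4/5.4 = 63%. The 2.0 points from other services remain and give an error of 5.2% (CV 0.5) or 5.0% (CV 1.0). The 63% is a ceiling, because as-needed dosing and prescriptions not settled at consent would escape.

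**The case against.** The strongest reply is that the PCA rule already covers the obvious route. Orthopaedic admissions in every arm get PCA dosed by weight and triggered by the patient. What remains is a pre-PCA window of unknown length, possibly nil, and unknown shares of patients at home or on other services. This stands, and it is why only those three parts are counted.

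It is also fair to say that the plan does not state who writes opioid orders. Calling the residents treating physicians makes it plausible that they write some, but that is an inference. So is the idea that other services know the arm. The fix therefore has to address whoever writes the orders.

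The gain is small: at the midpoint, 6.4% falls at best to 5.2%, or 5.4% to 5.0%. Nor does the fix touch patient expectation. Controls have no needle, while the procedure ends with "Remove needle-syringe construct and place bandage over injection site", so patients may guess their arm and change both their PCA demand and their own scores. Both points stand. They argue for a low grade, not for leaving the order of steps as it is.

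A reader might go further and infer that inpatient pain scores are biased because the operator may ask for them. The documents do not support that. Outpatients score themselves ("Patients treated as an outpatient will record these values themselves"). The section also refers to a "copy of recording form submitted with this application", which was not available and may name a recorder. The direction of any effect on Aim 1 is unknown too, since less opioid could raise pain.

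**Conclusion.** The point holds as a cheap improvement (COULD). Patient-only blinding, allocation at consent, operators who know the arm, and a single opioid-ordering rule limited to orthopaedic admissions are all in the text. Together they leave part of the Aim 2 total open to staff expectation.

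The size is probably modest: a fall of about 2% to 10% in an arm mean, and at the midpoint a 5% error of about 5.4% to 6.4%. This rests on six assumed bias inputs, an assumed CV and an assumed test, and on the two inferences about who writes orders and who knows the arm.

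A reader might infer that Aim 2 is invalid or that any opioid saving would be an artefact. The documents do not support that. They give no setting shares, no pre-PCA opioid volume and no evidence that staff ordered differently by arm.

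**What to change.** After consent and before the allocation is opened, whoever writes the initial analgesic orders enters them: emergency department or orthopaedic orders, PCA settings, and the usual discharge prescription if the patient is to go home. Later changes, including those by other services, are logged with time and reason.

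This reorders existing steps and adds a log. It needs no extra patients, staff or procedures, and leaves arms, doses and significance level unchanged. The cost is a short delay before the allocation is opened. It is best in place before the first patient, but could be adopted later for those still to be enrolled.

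Limits: as-needed dosing, other-service orders and discharge prescriptions settled later remain discretionary and can only be logged. Patient expectation is not addressed.

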## Risks

Risks associated with aspiration of the knee joint include:

- Pain
- Infection
- Inability to remove any fluid or blood from the joint
- The need to attempt another needle stick to place the needle in the correct position

Risks associated with injection of a local anesthetic in the joint include:

- Pain
- Infection
- Chondrolysis reported in vitro with bovine cartilage; no human studies support this finding.
- There have been no reported incidences of systemic issues associated with a single intra-articular knee injection of any local anesthetic

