## Rationale and Specific Aims

The primary objective of this study is to determine whether a patient with a tibial plateau fracture (non-displaced, displaced, depression type) will have decreased pain and narcotic analgesia requirements following an intra-articular injection of local anesthetic and aspiration of the knee. In order to determine whether this institution has an appropriate volume of tibial plateau fractures to adequately perform such a trial, we have reviewed our volume of tibial plateau fractures and have determined we have an adequate volume to conduct such a study. The primary outcome of the study could potentially guide future management of tibial plateau fractures at this institution and potentially systemically.

- a) Specific Aim 1: Examine the effect of hemarthrosis aspiration and intra-articular bupivacaine injection on recorded Numerical Rating Scale (NRS) pain scores for patients with tibial plateau fractures in the first 24 hours following injury.**
- Working Hypothesis: Hemarthrosis aspiration and intra-articular bupivacaine injection will significantly decrease subjective pain scores in the early post-injury period.*

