## **Reporting of Adverse Events or Unanticipated Problems involving Risk to Participants or Others**

Adverse event identification will be the responsibility of each member of the research team and to report same to one of the trauma surgeons, [name]; [name]; and [name]. Specifically, [name] will be responsible for reporting promptly to the IRB office.

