### **Study Withdrawal/Discontinuation**

If at any time during the course of the patient's treatment or data collection, the patient decides to withdraw from the study they may do so without any consequence. If the patient decides to withdraw after consent is given they may do so and will not be included in the study.

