### **Follow-up and Record Retention**

All records will be removed from secure server upon completion of the study. All paper records, if any, will be disposed of using Loyola approved system and receptacles.

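### Infection is a named risk of both needle procedures, but the plan sets no adverse event window or active enquiry, so an absence of reports cannot be read as evidence of safety

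*Combined protocol and SAP*

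**What the plan says.** The Risks section gives two lists. Infection appears under aspiration and again under the list that opens "Risks associated with injection of a local anesthetic in the joint include". The injection list also carries chondrolysis, qualified as "Chondrolysis reported in vitro with bovine cartilage; no human studies support this finding".

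Study Procedures fixes the timed measurements: "Subsequent VAS scores will be recorded at time points 0 (5 minutes after intervention), 2, 4, 6, 8, 12, 24 hours". Supplemental analgesia is recorded as it is given. Outpatients fill in the form themselves, and "Patients will be directed to bring the completed form with them to their regular clinic follow-up visit". No date is given for that visit, and no clinic visit is stated for admitted patients.

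The adverse event section says that "Adverse event identification will be the responsibility of each member of the research team", with onward reporting to the trauma surgeons and prompt notice to the IRB. It gives no list of events, no schedule of enquiry, and no start or end of the reporting period.

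Two other sections bear on what can be counted. Under Study Withdrawal/Discontinuation: "If the patient decides to withdraw after consent is given they may do so and will not be included in the study". Follow-up and Record Retention deals only with disposal of records: "All records will be removed from secure server upon completion of the study".

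**The concern.** The plan names a harm and then schedules nothing that would find it. The documents give no onset times, but on general clinical reasoning a joint infection after a needle stick would usually show itself later than 24 hours. After that point the plan depends on someone happening to report.

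Unprompted reporting may also differ by arm. On-call orthopaedic residents carry out the aspiration and injection, controls receive neither, and only patients are described as blinded. Staff who know that a knee was needled may attend to it differently. Patients treated with ORIF are eligible, and surgery brings an infection risk of its own, so an infection is hard to interpret unless all three arms are asked the same question.

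At stake is the balance of benefit and harm. The protocol hopes that its primary outcome may inform later care of these fractures. A reader weighing a pain benefit would look for the infection counts, and an empty column could be taken for reassurance that the data cannot give.

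**Working it through.** The plan has no safety endpoint, rate or target to reproduce. Its one design figure, the power for the 24-hour pain score, is not an input here.

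**Step 1: named harms against planned ascertainment.**

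| Item | What the plan provides |
|---|---|
| Infection (aspiration and injection) | No scheduled item |
| Chondrolysis (injection; in vitro only) | No scheduled item |
| Last timed measurement | Pain score at 24 hours |
| Later contact, outpatients | Undated clinic visit; only stated study use is return of the form |
| Later contact, admitted patients | None stated |
| Adverse event process | Duty on all team members; no definition, window or active enquiry |

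Aim 1's limit, "in the first 24 hours following injury", is the window for pain scores. It is not a safety window, and the plan has none.

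**Step 2: exposed patients.** Allocation is 22 per arm (Statistical Considerations). Aspirated: 22 + 22 = 44. Injected: 22.

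**Step 3: what zero events would show if every patient were followed.** The one-sided 95% upper limit p solves (1 − p)^n = 0.05, so p = 1 − 0.05^(1/n).

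- n = 22: 1 − 0.05^(1/22) = 12.7%
- n = 44: 1 − 0.05^(1/44) = 6.6%

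With 0.025 in place of 0.05 (two-sided), the limits are 15.4% and 8.0%.

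**Step 4: chance of seeing at least one event with complete ascertainment, 1 − (1 − p)^n.** The documents give no event rates, so the rates below are assumptions.

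| Assumed true rate | n = 22 | n = 44 |
|---|---|---|
| 0.5% | 10% | 20% |
| 1% | 20% | 36% |
| 2% | 36% | 59% |
| 5% | 68% | 90% |

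**Step 5: what incomplete ascertainment does.** If only a fraction s of events is recorded, the recorded count has rate s × p. Zero recorded events then bounds s × p at 12.7% (n = 22) or 6.6% (n = 44), so p is bounded only by 12.7%/s or 6.6%/s. Under the present plan s is unknown and may differ between arms, so no limit on p can be stated. Uniform enquiry is what brings s close to 1 and makes the Step 3 limits usable.

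**Step 6: provisions that make the gap wider.** A patient who withdraws because of a complication would leave the data set under the withdrawal rule. Because study records are removed at completion, an event surfacing later could not easily be linked back to its arm. Events have to be captured while the study is running.

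**The case against.** This is a small analgesia trial. Both aims concern pain and opioid use, and the point does not touch the primary analysis. The duty to identify adverse events has no end date, and patients may report problems through ordinary care. The limits of 12.7% and 6.6% come from the sample size and would remain after any change to data collection. All of this stands. It restricts what the fix can achieve, but it does not supply a common enquiry across arms.

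Several stronger readings are tempting, and the documents do not support them:

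- A reader might infer that every scheduled observation stops at 24 hours. That is true of the timed pain scores only; a later clinic visit is named for outpatients.
- A reader might infer that the trial would report the procedure as safe by default. No safety endpoint, analysis or conclusion is planned, and the sentence about informing later care refers to the primary outcome.
- A reader might infer that nobody asks about the knee at the clinic visit. The content of that visit is not described, and it is follow-up for a knee fracture.
- A reader might infer that outpatients have no number to call. The recording forms are not in the documents, and the consent and contact pages were removed before review, so this cannot be judged.
- A reader might take chondrolysis as an established human risk of the injection. The plan presents it as an in vitro finding only. Infection carries the point without it.

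**Conclusion.** The point holds in a limited form. Infection is named for both procedures, no defined safety assessment or adverse event window exists, and detection is unprompted in arms that staff can tell apart. Later infections could therefore be missed or found unequally, and an absence of reports must not be read as evidence of safety.

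Its size cannot be put as a number of missed events, because the documents give neither event rates nor onset times. What can be said is that complete ascertainment with zero events would still allow true rates up to 12.7% (22 injected) or 6.6% (44 aspirated), one-sided 95%, and that the present plan does not secure even that.

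The conclusion assumes that infection commonly appears after 24 hours, that at least some patients have ORIF (no proportion is given), and that the unseen forms hold no safety items. If they do, the gap narrows to the missing window and to admitted patients. This is a worthwhile, low-cost improvement; the pain comparison is unaffected.

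**What to change.** Amend Study Procedures and the adverse event section as follows.

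1. Define an adverse event window from the intervention (or, for controls, randomization) to the routine fracture follow-up visit, and state when that visit falls.
2. Record the same fixed items in all three arms: knee infection suspected or treated; repeat aspiration or washout; unplanned return for the knee; any other event. For outpatients, put them on the form already returned at that visit. For admitted patients, obtain them by chart check over the same window.
3. State how events before a withdrawal are counted, within what consent allows, so that complications do not disappear with the patient.
4. Report counts by arm with exact confidence limits. Note that zero events in 22 or 44 patients is compatible with true rates up to 12.7% or 6.6%, and state that the trial cannot exclude late cartilage damage.

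The cost is a few form items, a chart check and a short protocol amendment. The downside is slightly more data entry and a more modest safety statement. The change will not establish safety at this sample size; it makes the counts complete and comparable between arms.
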